### **7.3 LOST TO FOLLOW UP**

A participant will be considered lost to follow-up if the participant repeatedly fails to return for scheduled visits and is unable to be contacted by the study site.

The following actions must be taken if a participant fails to return to the clinic for a required study visit:

- The site must attempt to contact the participant and reschedule the missed visit as soon as possible, counsel the participant on the importance of maintaining the assigned visit schedule and ascertain whether the participant wishes to and/or should continue in the study.
- Before a participant is deemed lost to follow-up, the Investigator or designee must make every effort to regain contact with the participant (when possible, 3 telephone calls, and, if necessary, a certified letter to the participant's last known mailing address or local equivalent methods). These contact attempts should be documented in the participant's medical record.

Should the participant continue to be unreachable, the participant will be considered to have withdrawn from the study.

## 8 STUDY ASSESSMENTS AND PROCEDURES

- Study procedures and their timing are summarized in the SoA. Protocol waivers or exemptions are not allowed.
- Adherence to the study design requirements, including those specified in the SoA, is essential and required for study conduct.
- All screening evaluations should be completed and reviewed to confirm that potential participants meet all eligibility criteria. The Investigator will maintain a screening log to record details of all participants screened and to confirm eligibility or record reasons for screening failure, as applicable.
- Procedures conducted as part of the participant's routine clinical management (eg, blood count, urine tests) and obtained before signing of the ICF cannot be utilized for screening or baseline purposes even if they were performed within the timeframe defined in the SoA, Central laboratory analysis is required. See [Section 8.3.6](#) for pregnancy testing and [Section 8.3.5](#) for local Quantiferon Testing.
- In the event of a significant study-continuity issue (eg, caused by a pandemic), alternate strategies for participant visits, assessments, medication distribution and monitoring may be implemented by the Sponsor or the Investigator, as per local Health Authority/independent ethics committee requirements ([Section 10.8](#)).
- Safety/laboratory/analyte results that could unblind the study will not be reported to investigative sites or other blinded personnel until the study has been unblinded.
- Blood sampling details including volume for all laboratory assessments will be provided in the laboratory manual and the ICF.
- Repeat or unscheduled samples may be taken for safety reasons or for technical issues with the samples.

### 8.1 ADMINISTRATIVE AND GENERAL/BASELINE PROCEDURES

Baseline demographic characteristics will consist of:

1. Age (years)
2. Height (cm)
3. Weight (kg)
4. Race and Ethnicity
5. Gender, if applicable
6. Psoriasis history including date of symptom onset, date of the diagnosis, previous treatments (medication generic name, doses, clinical efficacy response [responder or no-responder], reason for discontinuation [side effects, lack of clinical efficacy, medication interaction with other concomitant therapy, remission/lack of symptoms, and other] and length of the therapy), and current treatments.
7. History of psoriasis in the family.

8. Concomitant disease such as diabetes mellitus, arterial hypertension, obesity, dyslipidemia, myocardial infarction, etc.
9. Details regarding current therapies and vitamins for concomitant therapies.
10. Smoking status, specifying if participant is current, former, or never smoker.

Study participant race or ethnicity will be collected in this study because analysis of results according to race/ethnicity are required by several Regulatory Authorities (eg, African American population for FDA in United States, Japanese population for the Pharmaceuticals and Medical Devices Agency [PMDA] in Japan or Chinese population for the National Medical Products Administration [NMPA] in China).

## 8.2 EFFICACY ASSESSMENTS

Planned timepoints for all efficacy assessments are provided in the SoA.

To minimize any bias, it is recommended participants to complete their PRO measures before clinician assessments and discussion of their clinical condition, treatment plan, AEs, and any other related topics that could influence participant's perception and feelings prior to responding to the questions. There will be a specific training on ePRO technology. For the ePRO data it is mandatory that a key person (for example research nurse) at each site is responsible for ePRO data collection, to optimize participant compliance and to ensure data completeness. Reason for non-completion will be documented in the eCRF.

### 8.2.1 Psoriasis area and severity index (PASI)

The PASI is an established measure of clinical efficacy for psoriasis medications (7). The PASI is a tool that provides a numeric scoring for participants' overall psoriasis disease state, ranging from 0 to 72. It is a linear combination of percent of surface area of skin that is affected and the severity of erythema, induration, and desquamation over four body regions.

The endpoints used are based on the percent reduction from baseline, generally summarized as a dichotomous outcome based on achieving over an X% reduction (or PASIX), where X is 50, 75, 90 and 100.

To calculate the PASI, the four main body areas are assessed: head (h), trunk (t), upper extremities (u) and lower extremities (l). These correspond to 10, 30, 20 and 40% of the total body area respectively.

The physician quantifies the percentage of the considered body area covered by plaque psoriasis. This percentage of psoriatic involvement is translated into a numerical value "Ax" for each body area: 0 = no involvement, 1 = <10%, 2 = 10 to <30%, 3 = 30 to <50%, 4 = 50 to <70%, 5 = 70 to <90%, and 6 = 90 to 100% involvement. These scores are noted Ah, At, Au, and Al in the formula below.

The signs of severity, erythema (E), induration (I) and desquamation (D) of lesions are assessed using a numeric scale 0-4 where 0 is a complete lack of cutaneous involvement and 4 is the severest possible involvement; scores are made independently for each of the areas, h, t, u, and l and represents a composite score for each area. An illustration of judging erythema follows: 0 = no erythema, 1 = slight erythema, 2 = moderate erythema, 3 = striking erythema, and 4 = exceptionally striking erythema.

The PASI score is calculated according to the following formula:

$$\text{PASI} = 0.1(E_h + I_h + D_h)A_h + 0.3(E_t + I_t + D_t)A_t + 0.2(E_u + I_u + D_u)A_u + 0.4(E_l + I_l + D_l)A_l$$

### **8.2.2 static Psoriasis Global Assessment (sPGA)**

The sPGA is a 5-point score ranging from 0 to 4, based on the physician's assessment of the average thickness, erythema, and scaling of all psoriatic lesions (14). The assessment is considered "static", which refers to the participant's disease state at the time of the assessments, without comparison to any of the participant's previous disease states, whether at Baseline or at a previous visit. A lower score indicates less body coverage, with 0 being clear and 1 being almost clear.

#### Erythema

- 0 Normal (post-inflammatory hyper/hypopigmentation may be present).
- 1 Faint, diffuse pink or slight red coloration.
- 2 Mild (light red coloration).
- 3 Definite red coloration (Dull to bright red).
- 4 Bright to Deep red coloration of lesions.

#### Induration (plaque elevation)

- 0 None.
- 1 Just detectable (slight elevation above normal skin).
- 2 Mild thickening (slight but definite elevation, typically edges are indistinct or sloped).
- 3 Clearly distinguishable to moderate thickening (marked definite elevation with rough or sloped edges).
- 4 Severe thickening with hard edges (marked elevation typically with hard or sharp edges).

#### Desquamation

- 0 No scaling.
- 1 Minimal focal scaling (surface dryness with some desquamation).
- 2 Predominately fine scaling (fine scale partially or mostly covering lesions).
- 3 Moderate scaling (coarser scale covering most or all of the lesions).

[figure not shown]
Overall Scoring resulting of the average of the Erythema, Induration and Desquamation score:

[figure not shown]
- Clear 0 = 0 for all three symptoms. Post-inflammatory hyper/hypopigmentation may be present.
- Almost clear 1 = mean  $>0, <1.5$ . Normal to pink coloration; just detectable (possible slight elevation above normal skin). No to minimal focal scaling.
- Mild 2 = mean  $\geq 1.5, <2.5$ . Pink to light red coloration; mild thickening (slight but definite elevation, typically edges are indistinct or sloped). Predominantly fine scaling.
- Moderate 3 = mean  $\geq 2.5, <3.5$ . Dull to bright red coloration; clearly distinguishable to moderate thickening; moderate scaling.
- Severe 4 = mean  $\geq 3.5$ . Bright to deep dark red coloration; severe thickening with hard edges; severe coarse scaling covering almost all or all lesions.

[figure not shown]
[figure not shown]
### 8.2.3 Body surface Area (BSA)

BSA will be calculated from the integrated BSA within the PASI assessment.

Percent BSA will be evaluated as the percent involvement of psoriasis on each patient's BSA on a continuous scale from 0% (no involvement) to 100% (full involvement), where 1% corresponds to the size of the patient's hand (including the palm, fingers, and thumb) (15).

### **8.2.8 Dermatology Life Quality Index (DLQI)**

The DLQI is one of the most widely used measures in dermatology populations to evaluate participants' Health-Related Quality of Life. It is a patient-reported outcome instrument consisting of 10 items exploring six dimensions: "Symptoms and feelings" (2 items), "Daily activities" (2 items), "Leisure" (2 items), "Work and school" (1 item), "Personal relationships" (2 items), "Treatment" (1 item). Each item is rated on a dichotomous: Yes/No and 3- and 4-point Likert/Likert-type scale for capturing skin symptom-related experiences over the previous weeks.

Scores are computed overall and for the six domains. The total DLQI score ranges from 0 to 30 which higher scores indicating better QoL. The instrument has good evidence of content validity and psychometric properties supporting its reliability, construct validity and responsiveness (16).

The DLQI questionnaires are provided in [Section 10.10.1](#).

### **8.3 SAFETY ASSESSMENTS**

This section presents safety assessments other than AEs which are presented in [Section 8.4](#).

Planned timepoints for all safety assessments are provided in the SoA.

#### **8.3.1 Physical examinations**

- The complete physical examination will consist of evaluation of the following systems: general, head, eyes, ears, nose, throat, neck, cardiovascular, lungs, abdominal, extremities, neurologic, psychiatric, skin, and musculoskeletal.
- The targeted physical exam will consist of evaluation of the following systems: general, eyes, throat, cardiovascular, lungs, abdominal, extremities, and skin, musculoskeletal.
- Complete and targeted physical examinations may be performed by a Doctor of Medicine, Doctor of Osteopathy, Physician's Assistant, or a Nurse Practitioner. A targeted physical examination may note any changes in the participant's condition since the last assessment and does not preclude examination of any of the body systems as clinically indicated.

### 8.3.2 Vital signs

- Vital signs include body temperature (°C), heart rate (beats per minute), and systolic and diastolic blood pressure (mm Hg) (before blood collection for laboratory tests).
- Blood pressure and pulse measurements will be assessed sitting with a completely automated device. Manual techniques will be used only if an automated device is not available.
- Blood pressure and pulse measurements should be preceded by at least 5 minutes of rest for the participant in a quiet setting without distractions (eg, television, cell phones).
- For blood pressure measurements, 3 consecutive blood pressure readings will be recorded at intervals of at least 1 minute. The average of the 3 blood pressure readings will be recorded.

### 8.3.3 Electrocardiograms

- Standard 12-lead ECGs are recorded after at least 10 minutes of rest in supine position using an electrocardiographic device. The electrodes will be positioned at the same place for each ECG recording throughout the study (eg, attachment sites of the leads will be visualized on a transparent paper).
- Triplicate 12-lead ECG will be obtained as outlined in the SoA (see [Section 1.3](#)) using an ECG machine that automatically calculates the heart rate and measures PR, QRS, QT, and QTcF intervals. [REDACTED].
- At each timepoint at which triplicate ECGs are required, 3 individual ECG tracings should be obtained within 5 minutes, with at least 1 minute between 2 replicates.
- The ECG should be recorded [REDACTED]  
[REDACTED]  
[REDACTED]  
• [REDACTED]  
[REDACTED].

- Each ECG consists of a 10-second recording of the 12 leads simultaneously, leading to:
  - A single 12-lead ECG (50 mm/s, 10 mm/mV) printout with heart rate, PR, QRS, QT, QTcF automatic correction evaluation using Fridericia formula (by the ECG device), including date, time, number of the participant, and at least 3 complexes for each lead. The Investigator should revise the results of the printout and his/hers medical opinion together with the automatic values will be recorded in the eCRF. This printout will be retained at the site. A second printout may be performed also, if needed.
  - A digital storage that enables potential further reading by an ECG central laboratory: each digital file will be identified by theoretical time (day and time Dxx Txx Hxx), real date and real time (recorder time), Sponsor study code, participant number (eg, 3 digits), and site and country numbers, if relevant. The digital recording, data storage, and transmission (whenever requested) need to comply with all applicable regulatory requirements (ie, FDA 21 code of federal regulations [CFR], Part 11).

#### **8.3.4 Clinical safety laboratory tests**

- See Appendix 2 ([Section 10.2](#)) for the list of clinical laboratory tests to be performed by central laboratory and the SoA ([Section 1.3](#)) for the timing and frequency.
- The Investigator must review the laboratory results, document this review, and record any clinically significant changes occurring during the study as an AE. The laboratory results must be retained with source documents. See Appendix 3 ([Section 10.3](#)) for abnormal laboratory results reporting. All laboratory tests with values considered clinically significantly abnormal during participation in the study or within 3 days after the last dose of study IMP should be repeated until the values return to normal or baseline or are no longer considered clinically significant by the Investigator.
  - If values do not return to normal/baseline within a period judged reasonable by the Investigator, the etiology should be identified, and the Sponsor notified.
  - All protocol-required laboratory tests, as defined in Appendix 2 ([Section 10.2](#)), must be conducted in accordance with the central laboratory manual and the SoA ([Section 1.3](#)).
  - If laboratory values from non-protocol specified laboratory tests performed at the institution's local laboratory require a change in participant management or are considered clinically significant by the Investigator (eg, SAE or AE or dose modification), then the results must be recorded in eCRF.

#### **8.3.5 Tuberculosis assessment and QuantiFERON®**

Medical history, including assessment of active TB, history of incompletely treated TB, undergoing treatment for latent TB or with current household contacts with active TB is considered part of the process to assess a participant's eligibility as outlined in [E 30](#) at the screening visit. All participants will have a screening test, the QuantiFERON® (an interferon gamma release assay, IGRA), performed centrally. If unable to obtain central lab results (eg, repeated test due to indeterminate result), an IGRA test could be obtained locally

(eg, T-spot®, QuantiFERON®), after consultation with the study medical monitor. Indeterminate IGRA may be repeated once during screening period and will be considered positive if retest results are positive or indeterminate.

Participants with a positive screening test will not be eligible for the study unless participants have documented completed appropriate active/latent TB treatment and consultation with a specialist has been obtained to rule out or treat active TB infection (for participants in the Czech Republic, see [Section 10.7.4](#)) and Sponsor approval has been granted in writing (Refer to exclusion criteria [E 30](#)).

#### **8.3.6 Pregnancy testing**

- Refer to [Section 5.1](#) Inclusion criteria for pregnancy testing entry criteria; the Investigator is responsible for review of medical history, menstrual history, and recent sexual activity to decrease the risk for inclusion of a woman with an early undetected pregnancy.
- Pregnancy testing (urine or serum as required by local regulations) should be conducted at prespecified intervals described in SoA during IMP treatment.
- Pregnancy testing (urine or serum as required by local regulations) should be conducted corresponding with the time frame for female participant contraception in [Section 5.1](#) Inclusion Criteria.
- Additional serum or urine pregnancy tests may be performed, as determined necessary by the Investigator, or required by local regulation, to establish the absence of pregnancy at any time during the participant's participation in the study.

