DAY	-28 to -11	1	15(±3)	29(±3)	57(±3)	85(±3)		113(±3)
WEEK	-4 to -1.5	0	2	4	8	12		16
Screening & Diagnostic tests								
Urine pregnancy test (WOCBP only) t		X		X	X	X		X
12-lead Triplett ECG u	X	X	X	X	X	X		X
Laboratory tests (include hematology- CBC with differential and liver chemistries- complete metabolic panel) v	X	X	X	X	X	X		X
Fasting lipids panel w		X		X		X		
Pharmacodynamics								

Procedure a	Screening period (up to 4 weeks and not less than 11 days before Day 1) b	Treatment period (12 weeks) c						Post-treatment period (4 weeks after last dose IMP)
		Baseline/ randomization					End of Treatment (EoT)	
VISIT	1	2	3	4	5	6		7
DAY	-28 to -11	1	15(±3)	29(±3)	57(±3)	85(±3)		113(±3)
WEEK	-4 to -1.5	0	2	4	8	12		16
Pharmacokinetic (PK) Assessments								
SAR441566 PK			X y	X z	X aa	X z	X aa	
Safety								
AE, SAE, TEAE and AESI review		←-----→						
Concomitant medication review		←-----→						

a Participants who discontinue IMP treatment prior to completing the 12-week treatment period should be assessed as per the EoT visit at the earliest opportunity and no later than 7 days from the last dose of IMP. After the EoT visit: (a) Participants who accept to stay on study without IMP intake: all remaining visits described in the SoA should be performed until the EoS, but only clinical assessments, AE and concomitant medication review and patient reported outcomes should be carried out at the study visits. (b) Participants who withdraw consent from the study: should have an EoS visit 4 weeks after their last dose of IMP.

b The screening period may be extended to 6 weeks (+/- 3 days) if participants are awaiting consultation with a specialist to rule out or treat active TB infection, or approval from Sponsor, according to [E 30](#).

c The morning IMP at visit days should be taken on site.

d Prior to randomization.

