- k When several assessments take place at the same visit, the following order is recommended: Patient Reported Outcome Measures (Questionnaires), Triplicate ECG (after 10min of rest), Blood sampling, Urine test (when applicable), IMP administration, Vital signs, Physical examination, Clinical assessments, IMP compliance check, verification of the Medication Intake Questionnaire (paper), Prior and concomitant medications, AE reporting, IMP dispensed for home administration. And during Post-IMP PK blood sampling visits, conclude with Triplicate ECG (after 10min of rest and within 15min prior to PK blood sampling), followed by PK blood sampling.
- l Dispensed with Medication Intake Questionnaire (paper).
- m Compliance will be assessed by the investigator by direct questioning, verifying the Medication Intake Questionnaire (paper), and counting returned tablets in each pack during the site visits and documented in the source documents and relevant form. Deviations from the prescribed dosage regimen must be recorded.
- n Questionnaire provided to the trial participant on D1 and at each visit, then returned by the participant at each visit and checked by the investigator to verify the IMP intake and potential adverse events.
- o Clinical assessments should be completed by the same physician for a given participant, if possible, to secure longitudinal comparison and avoid any bias.
- p BSA will be extracted from PASI assessment ([Section 8.2.3](#)).

s Refer to [Section 5.3.2](#) for further details.

*t* Refer to Section 8.3.6 – Pregnancy testing for instruction on timepoints

v Hematology: RBC, RBC indices, hemoglobin, hematocrit, thrombocyte count (platelets), leukocyte count (white blood cell count) with differential in absolute counts (including neutrophils, eosinophils, basophils, lymphocytes (including CD4 count), monocytes).

Clinical chemistry: Sodium, potassium, chloride, bicarbonate, blood urea nitrogen (BUN), creatinine, creatinine clearance, CPK, calcium, phosphate, total protein, albumin, alanine aminotransferase (ALT), aspartate aminotransferase (AST), alkaline phosphatase (ALP), total bilirubin, conjugated bilirubin, unconjugated bilirubin, glucose (non-fasting).

w Fasting total cholesterol, fasting triglycerides, HDL, and LDL. Participant must be fasting for 8 hours prior to laboratory testing (may consume water). A light meal will be provided by the site after the laboratory tests, lipids panel and pre-dose-PK.

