##### a) Male participants

Male participants are eligible to participate if they agree to the following during the study treatment period and for at least 3 months after the last administration of study IMP:

- Refrain from donating or cryopreserving sperm;

PLUS, either:

- Be abstinent from heterosexual intercourse as their preferred and usual lifestyle (abstinent on a long term and persistent basis) and agree to remain abstinent;

OR

- Must agree to use contraception as detailed below:  
A male condom and an additional highly effective contraceptive method (as described in [Section 10.4](#)), when having sexual intercourse with a woman of child-bearing potential (WOCBP) who is not currently pregnant.

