**b) Female participants**

- A female participant is eligible to participate if she is not pregnant or breastfeeding, and one of the following conditions applies:
  - Is a woman of non-child-bearing potential as defined in the [Section 10.4](#);  
OR
  - Is a WOCBP and agrees to use a contraceptive method that is highly effective (with a failure rate of <1% per year), preferably with low user dependency (as described in [Section 10.4](#)) during the study intervention period (to be effective before starting IMP) and for at least 3 months after the last administration of study IMP and agrees not to donate or cryopreserve eggs (ova, oocytes) for the purpose of reproduction during this period.

A WOCBP must have a negative highly sensitive pregnancy test (urine or serum as required by local regulations) at screening and a negative urine pregnancy test before the first administration of study IMP.

If a urine test cannot be confirmed as negative (eg, an ambiguous result), a serum pregnancy test is required. In such cases, the participant must be excluded from participation if the serum pregnancy result is positive.

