## **Handling of participants after permanent IMP discontinuation**

Participants who discontinue IMP treatment prior to completing the 12-week treatment period should be assessed as per the EoT visit at the earliest opportunity and no later than 7 days from the last dose of IMP. After the EoT visit:

- a) Participants who accept to stay on study without IMP intake: all remaining visits described in the SoA should be performed until the EoS, but only clinical assessments, AE and concomitant medication review and patient reported outcomes should be carried out at the study visits.
- b) Participants who withdraw consent from the study: should have an EoS visit 4 weeks after their last dose of IMP.

All cases of permanent IMP discontinuation must be recorded by the Investigator in the appropriate pages of the eCRF when considered as confirmed.

The recommended wash out period for SAR441566 is █ (>>5 x the half-life of SAR441566).

Property of the Sanofi group - strictly confidential

Page 57

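### Women of child-bearing potential who stop IMP early but stay on study have no clearly scheduled pregnancy test after the EoT visit

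*Protocol*

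**What the plan says.** **The testing rule.** Protocol 8.3.6 has two relevant bullets. The second asks for tests at the SoA intervals while the participant is on IMP. The third adds that testing "should be conducted corresponding with the time frame for female participant contraception" in Section 5.1. Inclusion criterion I 05 b) sets that time frame as the treatment period and "for at least 3 months after the last administration of study IMP and agrees not to donate or cryopreserve eggs".

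**The schedule.** The SoA (Protocol 1.3) places urine tests for women of child-bearing potential (WOCBP) at Weeks 0, 4, 8, 12 and 16 (EoS, Day 113 ± 3). Footnote t on that row refers the site to Section 8.3.6, "Pregnancy testing for instruction on timepoints". The row is under screening and diagnostic tests. The clinical assessments block holds PASI, sPGA and BSA.

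**Early IMP discontinuation.** Section 7.1.1 and footnote a require an EoT visit within 7 days of the last dose. Participants who then stay on study attend every remaining visit, but "only clinical assessments, AE and concomitant medication review and patient reported outcomes should be carried out at the study visits".

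**Status of the SoA.** Section 8 states: "Adherence to the study design requirements, including those specified in the SoA, is essential and required for study conduct".

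**The concern.** The list of assessments kept after EoT is introduced by the word only, and pregnancy testing is not on it. A site that follows the list would stop testing a woman who is still enrolled, still attending, and still inside the period in which she must use contraception. Section 10.4.2 gives the reason for that period: the drug may affect ova for up to 3 months.

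Footnote t does not help the site. It points to 8.3.6, where the SoA-based bullet is limited to the time on IMP and the contraception-based bullet names no timepoint. What is at stake is detection: a pregnancy that the woman has not noticed or reported could be missed at visits where a urine test was originally planned. No efficacy endpoint or estimand is involved.

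**Working it through.** The documents give no figure to reproduce, so the check is a comparison of texts followed by study-day arithmetic.

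**Inputs**
- EoT visit after early discontinuation: at most 7 days after the last dose (7.1.1, SoA footnote a). The EoT column includes a urine test.
- SoA test days after baseline: 29, 57, 85 and 113, each ± 3.
- EoS for completers: 4 weeks after the last dose.
- Contraception window: at least 3 months, taken here as 91 days (range 90 to 92).
- Stop days 15, 29 and 57 are illustrative.

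**Two readings of 7.1.1(a)**
- *Natural:* the restriction covers every visit after EoT, including EoS, so no scheduled test remains.
- *Narrower:* the restriction covers only the visits before EoS, so the Day 113 test stays.

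**Tests affected.** Latest EoT day = stop day + 7. Days after last dose = SoA day − stop day.

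| Last dose | EoT test by | Later SoA tests | Days after last dose | Dropped, natural | Dropped, narrower |
|---|---|---|---|---|---|
| Day 15 | Day 22 | 29, 57, 85, 113 | 14, 42, 70, 98 | 4 | 3 |
| Day 29 | Day 36 | 57, 85, 113 | 28, 56, 84 | 3 | 2 |
| Day 57 | Day 64 | 85, 113 | 28, 56 | 2 | 1 |

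**How far scheduled testing reaches**
- Natural reading: at most 7 of 91 days, which leaves 91 − 7 = 84 to 91 days without a scheduled test.
- Narrower reading, Day 29 stop: nothing between EoT and Day 113, which is 113 − 36 = 77 days or more.
- If the tests were kept at the remaining visits: 113 − 29 = 84 of 91 days for a Day 29 stop and 113 − 57 = 56 of 91 for a Day 57 stop. The whole window is covered for stops up to Day 113 − 91 = 22 (Day 110 − 92 = 18 to Day 116 − 90 = 26 across the visit window and month length).

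**Completers, for comparison.** With a last dose on Day 85, the window ends on Day 85 + 91 = 176. The last test is on Day 113, which is 176 − 113 = 63 days earlier (90 − 31 = 59 to 92 − 25 = 67). The third bullet of 8.3.6 is therefore not met for completers either, but they are clearly tested to 4 weeks after the last dose.

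**The case against.** **The text can be read to keep the tests.** Footnote t sends the site to 8.3.6, whose third bullet follows contraception rather than dosing and so still applies off IMP. The fourth bullet allows extra tests at any time during participation. The summary of changes for amendment 04 explains the restriction by assessments tied to IMP administration, with PK and blood draws as examples, and a urine test is not an obvious target. All of this stands and suggests an oversight. It does not produce a scheduled test: the third bullet gives no timepoint, the fourth is discretionary or depends on local rules, and the word only points the other way.

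**Other safeguards continue.** Contraception is required for 3 months. AE review and pregnancy collection run to EoS for this group, pregnancy is an AESI reportable within 24 hours, and known pregnancies are followed to outcome (8.4.1, 8.4.5, 8.4.8). This also stands and keeps the point minor.

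**Three stronger readings are tempting, and the documents do not support them.**
- *Testing completers only to EoS is too short.* The rationale for amendment 02 (Protocol 10.13.2) sets 4-weekly testing including EoS, so the endpoint looks deliberate. At the half-life of about 20 to 30 hours in Section 4.3, 4 weeks is 672/30 = 22.4 to 672/20 = 33.6 half-lives. Apart from the third bullet of 8.3.6, nothing says that EoS is too early.
- *Pregnancy collection must run for 3 months.* That bullet concerns testing only. Section 8.4.5 ends collection at EoS, as 8.4.1 does for AEs, and related post-study pregnancy SAEs are reportable if the investigator learns of them.
- *Women who stay are tested for less time than those who withdraw consent.* Footnote a(b) says that the latter "should have an EoS visit 4 weeks after their last dose of IMP", but Section 7.2 asks for a discontinuation visit only if possible. A visit that may not take place is not a sound benchmark.

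**Conclusion.** The point holds as a minor safety-monitoring gap. For WOCBP who stop IMP early and stay on study, no section clearly schedules a pregnancy test after EoT, although the protocol links testing to a window of at least 3 months and these women still attend visits that carry the test in the SoA. Between one and four tests are affected for the stop days shown, depending on the reading.

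The conclusion rests on taking clinical assessments to mean the SoA block of that name, on a 91-day quarter, and on the current 4-week follow-up (SAP 1.1 notes a 2-week follow-up for earlier enrollees). The figures are test counts and calendar days, not a measure of risk. The documents give neither the number of WOCBP nor their rate of IMP discontinuation, so the number affected cannot be estimated. For completers, the mismatch with the third bullet of 8.3.6 is a matter of wording.

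**What to change.** 1. In SoA footnote a(a) and Section 7.1.1, add to the assessments kept at the remaining visits, including EoS: urine pregnancy test (or serum where required locally) for WOCBP.
2. As a wording correction, rewrite the third bullet of 8.3.6 to name the SoA timepoints, so that testing runs to EoS and footnote t leads to an answer.

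The cost is a protocol amendment with matching consent and eCRF wording, and at most four urine tests (Weeks 4, 8, 12 and 16) per affected woman. No visit is added, the end-of-study definition does not move, and the efficacy analyses are unchanged. SAP 3.9 reports fast enrollment; if follow-up is largely complete, the wording is still worth carrying into later protocols.

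Extending pregnancy collection to 3 months after the last dose is optional. It would raise questions of database-lock timing and of collecting data from people who have left the study, and the correction above does not depend on it.
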